9.4 Causal Assessment

The degree of certainty of the relationship between AE and drug is determined by how well the event can be explained by the following factors: (1) known pharmacological properties, (2) comparable reactions observed previously with the drug or another member of its class, (3) an event with comparable substances commonly described in the literature as drug-related, (4) a chronological relationship between the event and drug intake, disappearance on withdrawal or recurrence on re-institution of the drug.

The investigator should make every effort to elucidate any AE and where necessary to assess its relationship to the study medication. The causal relationship should be assessed on the basis of the following categories:

Related: There is a reasonable causal relationship between study drug administration and the AE (definitely, probably, or possibly)

Not related: There is not a reasonable causal relationship between study drug administration and the AE (unlikely, no correlation).

9.5 Adverse Event Collection and Reporting Information

The following information should be captured for all AEs in the respective form of the eCRF: onset, duration, intensity, seriousness, relationship to study drugs, action taken, and treatment required. If treatment for the AE is administered, it should be recorded in the medical record.

All SAEs that occur following the date of signature of informed consent until 30 days after discontinuation of dosing must be reported to Alcedis GmbH, whether related or not related to study drug. Afterwards the investigator should report any SAE occurring after these aforementioned time periods, which is believed to be related to study drug.

9.6 Notification of (Serious) Adverse Events

All adverse events that occur with the study therapy must be entered in the case report form. Similarly, the duration and estimated severity of each adverse event must be noted. The assessment of an adverse event is made on the basis of the Common Terminology Criteria of Adverse Events (CTCAE) in Version 5.0 (Appendix 17.3)

If a CTCAE classification is not applicable, the adverse event must be described on the basis of the following classification:

Grade 1 = mild toxicity

Grade 2 = moderate toxicity

Grade 3 = severe toxicity

Grade 4 = life-threatening toxicity

Grade 5 = fatal toxicity

Each investigator must **inform Alcedis GmbH** (study office, address see below) **within 24 hours after becoming known** of the SAE that occur during the clinical study or within 30 days of the last dose of the study medication being received, irrespective of whether or not they are attributable to the preparations.

Each serious adverse event must be documented on the electronically available "**Serious adverse events report**" form. The SAE form must be printed and kept on file at the study site.

The completed form is automatically faxed (fax no. is filed automatically in the system) **to the sponsor and coordinating investigator**. In the event that electronic reporting is not possible, paper SAE forms in the investigator's file handed out at the beginning of the study are at the doctor's disposal for notification by conventional fax:

Study office:

Alcedis GmbH
[name]
[name]
Germany
[contact]
[contact]

These data must be entered in the eCRF afterwards.

Complete data on these events, including safety laboratory data, vital signs and efficacy data necessary to assess and monitor the safety of the funder's studied medicinal product, shall be collected and provided by the sponsor to Merck Healthcare Global Patient Safety as specified in the respective ISS Agreement.

If only limited information is initially available, follow-up reports are required.

The initial report must be followed **within 5 days** by a detailed written communication (in English) containing a precise description of the side effects, all countermeasures taken and their outcome. In the event of death, if an autopsy has been performed, a copy of the autopsy report should be attached.

If an ongoing SAE changes in its intensity or relationship to study drug or if new information becomes available, a follow-up SAE report should be sent within 24 hours using the same procedure used for transmitting the initial SAE report.

The Sponsor will send appropriate safety notifications to Health Authorities in accordance with applicable laws and regulations.

When specifically required by regulations and guidelines, the Sponsor/designee will provide appropriate Safety Reports directly to the concerned lead IEC/IRB and will maintain records of these notifications. When direct reporting is not clearly defined by national or site-specific regulations, the Investigator will be responsible for promptly notifying the concerned IEC/IRB of any Safety Reports provided by the Sponsor/designee and of filing copies of all related correspondence in the Investigator Site File.

For studies covered by the European Directive 2001/20/EC, the Sponsor's responsibilities regarding the reporting of SAEs/SUSARs/Safety Issues will be carried out in accordance with that Directive and with the related Detailed Guidance documents.

9.7 *Pregnancy*

WOCBP and male patients with partners of childbearing potential must agree to always use a highly effective form of contraception according to CTFG during the course of this study and for at least 3 months after completion of study therapy. Birth control methods which may be considered as highly effective can achieve a failure rate of less than 1% per year when used consistently and correctly. Pregnancy tests should be performed at baseline, prior to the first cycle and subsequently every 4 weeks during pre-randomization part and randomized part.

Before study enrollment, WOCBP must be advised of the importance of avoiding pregnancy during study participation and the potential risk factors for an unintentional pregnancy. All WOCBP should be instructed to contact the investigator immediately if they suspect they might be pregnant (e.g., missed or late menstrual period) at any time during study participation. The patient must sign an informed consent form documenting this discussion.

The minimum sensitivity of the pregnancy test must be 25 IU/L or equivalent units of hCG. If the pregnancy test is positive, the patient must not receive study treatment and must not be enrolled in the study.

If, following initiation of the clinical trial, it is subsequently discovered that a study patient is pregnant or may have been pregnant at the time of investigational product exposure the study treatment will be permanently discontinued in an appropriate manner. The investigator must immediately notify Alcedis GmbH of a pregnancy occurring during the conduct of the clinical trial including at least 2 months after last study administration and record the pregnancy on the Clinical Trial Pregnancy Reporting Form (not an SAE form). Initial information on a pregnancy must be reported within 24 hours of investigator/site awareness of the event to Alcedis GmbH and Merck, and the outcome information provided once the outcome is known. Completed Pregnancy Surveillance Forms must be forwarded to Alcedis GmbH according to SAE reporting procedures.

10 Statistical Methods

10.1 *Statistical Objectives*

The primary objective is to evaluate efficacy in terms of PFS according to RECIST version 1.1 criteria in experimental and control arms.

Secondary Objectives are evaluation of:

- OS in experimental and control arms after the date of randomization
- TFTS in experimental and control arms after the date of randomization
- PFS rate 1 year after the date of randomization
- Depth of response in terms of reduction of tumor mass in experimental and control arms after start of 1st line treatment
- Percentage of patients with metastasis resections in experimental and control arms after start of 1st line treatment
- ORR defined as patients with partial or complete response (CR + PR) in experimental and control arms after start of 1st line treatment
- Safety profile according to CTCAE, Version 5.0 criteria in experimental and control arms to be recorded from the date of signature of Informed Consent

Optional exploratory objectives are

- To identify driver mutations (e.g. BRAF, PI3K-AKT-mTOR etc.), in patients with PD under cetuximab therapy which remain RAS wild-type in liquid biopsy
- To compare PFS in patients with conversion to *RAS* wild-type in ddPCR and BEAMing with those patients showing conversion to *RAS* wild-type in ddPCR but not in BEAMing

10.1.1 Primary Variable

PFS, defined as being the time between date of randomization until the date of progression according to RECIST v.1.1 criteria or date of death from any cause, whichever occurs first. Any change of *RAS* mutation status without disease progression according to RECIST v.1.1 is not considered a PFS event. PFS should be censored, in patients without a PFS event, on the last date they were known to be alive and progression-free (last valid tumor assessment) or at the start of new anti-tumor therapy. Patients becoming eligible for surgery during study treatment, will not be censored for PFS at this event (resection).

10.1.2 Secondary Variables

- OS, defined as time from date of randomization until death from any cause; OS should be censored, in patients without an OS event, on the last date they were known to be alive.
- TFTS, is defined as time from date of randomization to failure of treatment strategy defined as treatment discontinuation for any reason, including disease progression, withdrawal of consent, treatment toxicity, patient preference, loss to follow up or death from any cause.
- PFS rate 1 year after date of randomization, derived by Kaplan-Meier method (defined as the estimated rate of patients with progression or death from any cause 1 year after date of randomization)
- Depth of response (DpR) in terms of reduction of tumor mass in experimental and control arms, defined as the percentage of tumor shrinkage, based on longest diameters of all target lesions or reconstructed volume, observed at the lowest point (nadir) compared to baseline. The time for DpR assessment varies between patients relating to the individual achievement of maximal tumor shrinkage, which typically occurs 4–6 months after the start of 1st-line therapy. DpR varies between 100% (= all target tumor lesions have disappeared) and 0% (=no change in tumor size) and has a negative value in cases of increased tumor volume.
- Percentage of patients with metastasis resections, defined as percentage of patients with complete resection of primary tumor and metastases (R0-resection), at any time after the start of 1st line therapy until the end of the treatment strategy.
- ORR, defined as the proportion of randomized patients with CR or PR as best response since start of 1st line therapy.
- Safety, defined as all SAEs regardless of causality, and non-serious adverse events according to CTCAE Version 5.0 criteria, that are definitely, probably, or possibly related to the administration of any study treatment, or that cause permanent discontinuation of treatment, recorded from the date of signature of Informed Consent.

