2.3.2 Clinical Efficacy Summary and *RAS* status

Cetuximab as a single agent or in combination with chemotherapy was investigated in 5 randomized controlled clinical studies and several supportive studies. The 5 randomized studies investigated a total of 3734 patients with metastatic colorectal cancer, in whom EGFR expression was detectable and who had an ECOG performance status of ≤ 2 . In all of these studies, cetuximab was administered once a week with an initial dose of 400 mg/m² and 250 mg/m² subsequently.

CRYSTAL, a randomized study in patients with metastatic colorectal cancer who had not received prior treatment for metastatic disease, compared the combination of cetuximab and irinotecan plus infusional 5-fluorouracil/folinic acid (FOLFIRI) to the same chemotherapy (FOLFIRI) alone. Median PFS and OS was 8.9 and 19.9 months, respectively, for patients in the cetuximab arm, and 8.0 and 18.6 months, respectively, for patients receiving chemotherapy only. Retrospective efficacy analysis according to *RAS* status (wild-type or mutant) is shown in Table 1.

Variable/ statistic	RAS wild-type population		RAS mutant population	
	Cetuximab plus FOLFIRI	FOLFIRI	Cetuximab plus FOLFIRI	FOLFIRI
	(N=178)	(N=189)	(N=246)	(N=214)
OS				
months, median	28.4	20.2	16.4	17.7
(95% CI)	(24.7, 31.6)	(17.0, 24.5)	(14.9, 18.4)	(15.4, 19.6)
Hazard Ratio (95% CI)	0.69 (0.54, 0.88)		1.05 (0.86, 1.28)	
p-value	0.0024		0.6355	
PFS				
months, median	11.4	8.4	7.4	7.5
(95% CI)	(10.0, 14.6)	(7.4, 9.4)	(6.4, 8.0)	(7.2, 8.5)
Hazard Ratio (95% CI)	0.56 (0.41, 0.76)		1.10 (0.85, 1.42)	
p-value	0.0002		0.4696	
ORR				
%	66.3	38.6	31.7	36.0
(95% CI)	(58.8, 73.2)	(31.7, 46.0)	(25.9, 37.9)	(29.6, 42.8)
Odds Ratio (95% CI)	3.1145 (2.0279, 4.7835)		0.8478 (0.5767, 1.2462)	
p-value	<0.0001		0.3970	

Table 1: Efficacy according to *RAS* status

The importance of *RAS* as a predictive marker for the efficacy of cetuximab treatment in mCRC was supported by other clinical trials.

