10.3 Statistical Methods

In general summary statistics (n, mean, standard deviation, median, minimum and maximum for continuous variables, and number of patients and percentage in each category for categorical variables) will be provided.

Time to event variables will be summarized using Kaplan-Meier methods as well as a Cox-regression model taking into account the following stratification factors: conversion to RAS wildtype within the first 8 weeks from start of 1st line therapy or later. Other factors (such as e.g. ECOG PS or location of metastases) will be taken into account in a multivariable Cox regression as well. Details will be specified in the SAP.

All analyses except for the log-rank test for the primary endpoint will be of exploratory manner. Hence no adjustment of the type I error rate is necessary.

All efficacy variables (primary and secondary endpoints) will be analyzed in the mITT and the PP set.

The SP set will be used for the analyses of the safety variables. Safety analysis includes:

- System Organ Class (SOC) and Preferred Terms (PT) according to the Medical Dictionary for Regulatory Activities (MedDRA). The most current MedDRA version, which is valid at the time of analysis, will be used.
- Causality of AE
- Outcome of AE
- AEs leading to death
- AEs leading to treatment/study discontinuation
- All SAEs

Details of the analyses will be given in the SAP.

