10.4 Sample Size

Data from historical studies suggest the 12-months PFS rate of FOLFIRI in RAS-mutant mCRC to be in a range of 25-27%. In CRYSTAL study PFS-rate at 12 months of FOLFIRI + Cetuximab in left-sided RAS wild-type mCRC was 50% (HR = 0.56).

Assuming that the difference in PFS at 12 months between the experimental and control arms will amount to 20%, which means an increase from 30% to 50% (Hazard ratio = 0.5757), 2 x 58 patients are to be randomized and 107 PFS events are needed if alpha error is 5% (0.05) and beta error is 20% (0.2). With a recruitment period of 18 months, a drop-out rate of 0.25% per month the 107 events are expected after a total follow-up time of 52 months assuming an exponential distribution.

Based on our data, the conversion rate is 80%. Assuming this conversion rate, 144 patients need to be screened to achieve 116 patients for the randomization. The screening will be continued until 116 patients are randomized.

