#### Secondary objectives:

- OS in experimental and control arms from date of randomization,
- Time to failure of treatment strategy (TFTS) in experimental and control arms after randomization,
- PFS rate one year after date of randomization,
- Depth of response (DpR) in terms of reduction of tumor mass in experimental and control arms after of first-line treatment,
- Metastatic resections in experimental and control arms after first-line treatment,
- ORR defined as proportion of patients with partial response (PR) or complete response (CR) as best response in experimental and control arms after start of first-line treatment,
- Safety profile according to the National Cancer Institute's (NCI) Common Terminology Criteria of Adverse Events (CTCAE) version 5.0 criteria in experimental and control arms recorded from date of signature of informed consent.

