## 4 Methods of analysis

### 4.1 Hypotheses

Initially, the hypothesis of this study was to show that the difference in PFS at twelve months between the experimental arm and control arm would amount to 20% meaning an increase from 30% to 50% (Hazard ratio = 0.5757). The estimated number of patients screened was 144 and the estimated number of randomized patients was 116.

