#### 4.3.5 Primary objective

For the analysis concerning the primary objective the following three listings are given and considered for PFS:

- RECIST assessments (Listing 23.1) and observation of measurable and non-measurable (Listing 23.2) lesions via computer tomography (CT).

In addition,

- a listing containing PFS, OS, and TFTS (Listing 24)

will be created.

Furthermore,

- a Kaplan-Meier plot for PFS (Figure 2)

will be presented.

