#### 4.3.6 Secondary objectives (excluding safety)

Due to the small number of patients neither all secondary objectives will be analyzed, nor full Kaplan-Meier methods will be applied to time-to-event analyses. Only OS, TFTS, and ORR will be considered. The first two named will be shown in the listing containing the primary objective PFS above, and in addition two Kaplan-Meier plots will be presented:

- a Kaplan-Meier plot for OS (Figure 3)
- a Kaplan-Meier plot for TFTS (Figure 4)

The remaining derived variable, ORR, will be given in

- a table displaying responses to study treatment together with ORR (Table 2).

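### Does the inverted wording of the 1-year PFS rate in Protocol 10.1.2 require a correction to the plan?

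*Protocol*

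**What the plan says.** Protocol 10.1.2 lists the PFS rate at 1 year as a secondary variable, estimated by Kaplan-Meier and "defined as the estimated rate of patients with progression or death from any cause 1 year after date of randomization". No other section of either document defines this rate. Protocol 3.2.2 and 10.1 and SAP 3.4 only name it.

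The planning sections use a 12-month PFS rate whose increase is a benefit. Protocol 10.4 assumes a 20-point difference, "which means an increase from 30% to 50% (Hazard ratio = 0.5757"), and SAP 4.1 repeats it: "meaning an increase from 30% to 50% (Hazard ratio = 0.5757"). Protocol 10.4 also cites historical rates of 25-27% for FOLFIRI in RAS-mutant disease and 50% for FOLFIRI plus cetuximab in left-sided RAS wild-type disease.

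On the status of the endpoint, Protocol 10.3 states: "All analyses except for the log-rank test for the primary endpoint will be of exploratory manner". SAP 4.2 reports that enrolment closed with seven patients. SAP 3.4 still lists "PFS rate one year after date of randomization" among the secondary objectives, but SAP 4.3.6 says "Only OS, TFTS, and ORR will be considered". For PFS itself, SAP 4.3.5 plans listings and "a Kaplan-Meier plot for PFS (Figure 2").

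**The concern.** A PFS rate at a fixed time normally means S(t), the estimated proportion alive without progression. The bracket in Protocol 10.1.2 describes its complement. An analyst who followed it to the letter would report a number that falls when treatment works, while every benchmark in Protocol 10.4 rises when treatment works. A control-arm result set beside the historical 25-27% would be on the wrong scale.

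The SAP would be the natural place to repair this, but SAP 4.12 defines only PFS, OS, ORR and TFTS. The objective remains listed in SAP 3.4, and Version 2.0 of the SAP added a PFS curve from which a 1-year value could be read. At first sight, then, the plan keeps an objective whose only definition points the wrong way.

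**Working it through.** **Inputs.** 12-month PFS of 30% (control) and 50% (experimental), hazard ratio 0.5757, 107 events, 2 x 58 patients, 18 months' recruitment, drop-out 0.25% per month, 52 months in total, exponential PFS (all Protocol 10.4; the rates and hazard ratio also in SAP 4.1). Two-sided alpha 0.05 and power 80% (Protocol synopsis).

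**Step 1: which reading the planning uses.** Under exponential PFS, HR = ln S_exp(12) / ln S_ctrl(12).

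- Event-free reading: ln(0.50)/ln(0.30) = (-0.6931)/(-1.2040) = 0.5757. This is the stated figure.
- If 30% and 50% were event rates: ln(0.50)/ln(0.70) = (-0.6931)/(-0.3567) = 1.943, which would mean harm.

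The planning rates are event-free proportions.

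**Step 2: the rest of the sample size on that reading.**

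- Monthly hazards are 1.2040/12 = 0.1003 (control) and 0.6931/12 = 0.0578 (experimental), with a drop-out hazard of 0.0025.
- With uniform accrual over 18 months and k the sum of event and drop-out hazards, expected events per arm at 52 months are 58 x (hazard/k) x {1 - [exp(-34k) - exp(-52k)]/(18k)}. This gives 55.8 + 51.2 = 107.0, matching the 107 stated.
- Required events are 103 by Schoenfeld and 109 by Freedman (108.2 before rounding up), on either side of 107.

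The sample size is coherent and takes nothing from the bracket in 10.1.2.

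**Step 3: the bracket applied literally to the planned effect.**

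| | Control | Experimental | Difference |
|---|---|---|---|
| Event-free, S(12) | 30% | 50% | +20 points |
| Bracket, 1 - S(12) | 70% | 50% | -20 points |

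The hazard ratio is the same in both rows: ln(1 - 0.50)/ln(1 - 0.70) = 0.5757. Only the reporting scale flips. The experimental value does not move, because 50% is its own complement. The 1.943 in Step 1 shows which way Protocol 10.4 must be read. It is not an effect of the wording in 10.1.2.

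**Step 4: direction check against the historical data.** Protocol 2.3.2 says that efficacy by RAS "status (wild-type or mutant) is shown in Table 1". That table gives medians, not 12-month rates, so an exponential curve is assumed.

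- RAS-mutant FOLFIRI, median 7.5 months: S(12) = 0.5^(12/7.5) = 33%, event rate 67%. The cited 25-27% lies on the event-free side.
- Read as event-free, 25-27% implies a median of 6.0-6.4 months. Read as an event rate, it implies 26.4-28.9 months.

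This supports the direction only. The 6.0-6.4 months falls below the table's 95% interval of 7.2 to 8.5, and the table is not split by tumour side.

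**Step 5: where the rate would be used.**

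- SAP 4.3.6 analyses OS, TFTS and ORR only.
- SAP 4.7 marks point and interval estimates as not applicable.
- SAP 4.12 defines the four derived variables that are reported and no others. Depth of response and metastasis resection are also listed in SAP 3.4 and also have no definition there.
- SAP 4.23 discloses that some objectives are not considered.
- SAP section 10 lists no 1-year rate.
- Figure 2 is titled progression-free survival, so the curve already runs in the right direction.

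No planned table, listing or figure uses the bracket.

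**The case for a change.** The best case for a change is that a definition should not depend on the reader overriding it. This is the only definition of the endpoint, it is inverted, the objective is still listed, and SAP 4.23 does not name it as dropped. A PFS curve has been added, and one line in SAP 4.12 or 4.23 would settle the matter.

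Two parts of this stand: the wording is wrong, and nothing else in either document corrects it. The rest does not lead to a change. The SAP names the three non-safety secondary endpoints it keeps, so the 1-year rate is excluded as clearly as depth of response and resection are. Adding a definition to SAP 4.12 for a quantity the SAP does not compute would be the less consistent choice. Harm would require someone to read a 12-month value off Figure 2 by eye and then label it with the protocol's bracket, and no section plans that. Correcting Protocol 10.1.2 itself would need an amendment submitted to ethics committees and competent authorities (Protocol 15.3), which is out of proportion to a parenthesis in an exploratory endpoint that is no longer analysed.

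**Conclusion.** This is a genuine clerical slip, and correcting it brings no gain. The bracket in Protocol 10.1.2 describes 1 - S(12) where S(12) is plainly meant. On the planned effect that is 70% versus 50% instead of 30% versus 50%, with the hazard ratio still 0.5757. The primary PFS definition, the log-rank test, the 107 events, the 116 patients and Figure 2 are all unaffected, and the number of planned outputs that change is zero.

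The conclusion assumes that the SAP is followed as written, with no 1-year rate tabulated. If a 1-year PFS value is nevertheless quoted in the report, the label and the Kaplan-Meier estimator already point a statistician to the right quantity: the estimated proportion alive and progression-free 1 year after randomization.
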